At the initial visit and at all follow-up visits, participants will be asked to produce 5 ml of saliva. Our work in previous desensitization studies has demonstrated that even children as young as 6 years can produce this volume of saliva. Egg-specific salivary IgA will be determined by ELISA

5. Statistical Considerations

Given that previous studies in adults have attributed at least 50% improvement in the ability to tolerate egg ⁽⁷⁵⁾ with an α of 0.05 and a power ($1 - \beta$) of 0.80, a sample of 17 cases and 17 controls will be recruited. Statistical analyses will be performed using paired t-tests. A P value of <0.05 will be considered significant.

Descriptive statistics of the variables including means, standard deviations and frequencies were computed for all study variables. The concentrations of egg -sIgE and sIgG , the weal size , Mast cell, salivary IgA, T cell and DNA methylation status at the different study time-points will be compared with their baseline values using the one-sample paired t-test and to the control using a 2 sample t-test .

Multiple regression models will be used to assess factors associated with response to desensitization (i.e. baseline demographic characteristics; gender; age; baseline basophile

activation; T cell status, baseline SPT and specific IgE, salivary IgA, and DNA methylation status,).

6. Ethical Considerations

In the consent form given at study enrolment, participants will be advised that they will be randomly assigned to either desensitization treatment or observation alone for one year, (appendix B). Participants will also be advised that their data will be shared only among the study members. Participants who will be at the control group will be told that they will be offered the desensitization protocol one year after study entry.

7. Participant Confidentiality and Record Retention

All participants will be assigned a unique study code that will be used on all study documents. The link between the participants' code and their name will be stored on a password protected computer in the MUHC's Centre for Innovative Medicine, which is a restricted access unit. All study documents will be kept in a locked filing cabinet in the Centre for Innovative Medicine. Only members of the study team, and authorized oversight bodies will be allowed access to the study documents.

Study documents will be kept at the Centre for Innovative Medicine for two years after the end of the study, then transferred to Iron Mountain for long-term storage off-site. All study documents will be stored for 25 years

8. Research Deliverables and Milestones

Timeframe	Deliverables	Milestones
------------------	---------------------	-------------------

01/17 – 03/18	Develop sampling frame; ethics approval;	Ready to recruit participants
03/18 –07/20	Collect data from participants	12 weeks of data collection in treated participants completed
07/20– 12/24	Knowledge translation activities: dissemination workshops & manuscript preparation	Preparation of abstracts and manuscript

9. Requirement for networking across Disciplines and Sites

Our researchers have a legacy of working across disciplines, across sites, and across sectors. For this study, we have assembled a multi-institutional research team with cross-disciplinary expertise [name] (Montreal Children’s Hospital, McGill University) and [name] (Montreal Children’s Hospital) and [name] (f Department of Pediatrics, University of Alberta, Edmonton, Canada)bring expertise in clinical immunology to the research team. [name] (Montreal General Hospital) will bring expertise in the field of clinical allergy and together with the co-investigator, [name], a biostatistician, will assisted with the study design and will supervise the statistical analyses. [name] (Departments of Microbiology & Immunology and Medicine, McGill University, Montreal, Quebec) will contribute their expertise in the areas of T cell phenotyping and DNA methylation status. Epidemiologic and

biostatistician skills are essential to undertaking this program of research and are represented in the persons of [name] (McGill) and Mr .[name] (both Msc in Epidemiology). [name] will also be responsible for the laboratory evaluation of CD63 levels. Finally, as incorporated in our protocol, we will share the results of this research with representatives of key constituencies involved in the data collection –patients with food allergies and their families, physicians and allied professionals (e.g. nurses) through scientific meetings, our website and publications in medical journals.

10. Organization of Research Team

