Cow milk allergy (CMA) and egg allergies are the most common food allergies in children and recent reports suggest that rates of resolution are considerably lower than previous estimates.⁽¹⁵⁻¹⁷⁾ Further, both CMA and egg allergy are associated with severe anaphylaxis^(18;19) and due their ubiquitous use in our diet are almost impossible to strictly avoid.⁽²⁰⁻²²⁾ In line with these, several studies suggest that quality of life of patients with milk/egg allergy and their families is severely impaired.⁽²³⁻²⁵⁾

With the support of AllerGen NCE and CIHR we have initiated in 2014 the first cross Canada study to assess milk desensitization. This study now includes almost 50 patients,

and our preliminary results reveal an almost 80% success rate . We are now proposing to initiate an egg desensitization study based on the expertises, recruitment skills and data collected in our first 2 years of milk desensitization.

We hypothesize that there will be at least 50% improvement in the ability to tolerate egg. E.g. a child that was able to tolerate only 40 mg of merengue will be able to tolerate at least 60 mg subsequent to desensitization

The trial design is an RCT aiming to demonstrate superiority of the desensitization protocol to an avoidance strategy regarding the tolerated quantity of egg . The ratio of patients to control is 1:1 . Patients will be block randomized in groups of 2 according to age and sex.

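### The 80% power for 17 per arm rests on a 50% gain in tolerated egg, not on the primary variable (300 mg at 1 year), and no suitable between-arm test is named for that variable

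*Combined protocol and SAP*

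**What the plan says.** Section 5 (Statistical Considerations) gives the sample size in one sentence. Because "previous studies in adults have attributed at least 50% improvement in the ability to tolerate egg", with α of 0.05 and power of 0.80, "a sample of 17 cases and 17 controls will be recruited". The source cited is reference 75. The next sentence reads "Statistical analyses will be performed using paired t-tests". A later sentence, confined to sIgE, sIgG, weal size, mast cell, salivary IgA, T cell and methylation measures, compares each with its own baseline by a paired t-test and "to the control using a 2 sample t-test". Multiple regression is planned for predictors of response; the factors listed are baseline characteristics, and study arm is not among them.

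Section 3.ii (Why Egg) uses the same phrase for the hypothesis: "We hypothesize that there will be at least 50% improvement in the ability to tolerate egg". Its example is that "a child that was able to tolerate only 40 mg of merengue will be able to tolerate at least 60 mg". It states the trial's aim as "superiority of the desensitization protocol to an avoidance strategy regarding the tolerated quantity of egg", with 1:1 allocation and randomization in blocks of 2 by age and sex.

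Section 4 (Variables measured, item A) defines the primary variable as qualitative, assessed 1 year after the start of the trial: total desensitization (300 mg), partial (30-300 mg) or failed (below 30 mg). Only total desensitization is a success. The nearest dose measure, the minimum dose that triggers symptoms, is secondary.

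**The concern.** The trial is sized on one quantity and judged on another. Section 5 and the hypothesis in section 3.ii concern a relative gain in milligrams tolerated; the primary variable concerns reaching a fixed 300 mg. A child can meet the hypothesis without becoming a success, so power for the first says nothing definite about power for the second.

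The analysis has the same gap. A superiority trial needs a stated comparison of the two arms on its primary variable, and section 5 offers none that suits a categorical outcome. The choice between a test of 300 mg success, an ordinal test and a t-test on dose would be left until after the data are seen. Nor does the plan say what difference in 300 mg success 34 children can detect.

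**Working it through.** **1. Can the plan's figure be reproduced?** Inputs in section 5: α 0.05, power 0.80, 17 per arm, 50% improvement. Missing: standard deviation, success rate in each arm, sidedness. The 17 therefore cannot be reproduced; it can only be solved backwards (two-sided 5% assumed throughout).

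- Two-sample t-test: 17 per arm has 80% power for a difference of 0.991 SD (normal approximation: (1.960 + 0.842) × √(2/17) = 0.961). A 50% gain then requires an SD of 0.5/0.991 = 0.505 times the baseline mean or, on the log scale, ln(1.5)/0.991 = 0.405/0.991 = 0.409.
- Two proportions 50 percentage points apart: the usual formula gives 11 to 15 per arm uncorrected and 15 to 19 with continuity correction. Exactly 17 arises for 10% vs 60% (or 40% vs 90%), rates that appear nowhere in the plan.

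**2. Does a 50% gain mean success?** On one scale, x × 1.5 ≥ 300 requires x ≥ 200 mg. From 40 mg, success needs 300/40 = 7.5 times the starting dose, against 1.5 times in the example. A child at 60 mg is in the partial band. If the 60 mg is powder, it is 36 mg of protein at Appendix B's ratio (6.04 g per 10 g) or 45 mg at that in section 4, Food challenges (6 g per 8 g): still partial.

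**3. Power for 300 mg success, Fisher's exact test, 17 per arm.** Power = Σx Σy Bin(x; 17, p_control) × Bin(y; 17, p_treated), summed over the tables with two-sided p ≤ 0.05. For example, with no control successes, 5 of 17 treated successes are needed (p = 2 × 6188/278256 = 0.044; with 4, p = 0.10), and P(at least 5 of 17 at a 37% rate) = 0.814. All rates below are assumptions.

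| Treated | Control 0% | 5% | 10% | 20% | 30% |
|---|---|---|---|---|---|
| 80% | >99% | >99% | 99% | 94% | 79% |
| 70% | >99% | 99% | 95% | 79% | 56% |
| 60% | >99% | 94% | 83% | 56% | 31% |
| 50% | 98% | 81% | 63% | 32% | 14% |
| 40% | 87% | 61% | 39% | 14% | 5% |

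Pairs giving about 80%: 37% vs 0% (81.4%), 50% vs 5% (81.3%), 59% vs 10% (81.0%), 71% vs 20% (81.1%).

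**4. Power if tolerated dose were primary.** Two-sample t-test on log dose, 17 per arm, no change in controls, at the minimum gain of 50%: 82% if the SD of log dose is 0.4, 63% if 0.5, 37% if 0.7, 21% if 1.0. These SDs are assumptions; the plan gives none.

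**5. Source of the 50%.** The title of item 75 in the reference list concerns relaxation therapy and hypnotizability in chronic urticaria, so no egg source for the figure is visible.

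**The case against.** *The 50% is a floor.* Sections 3.ii and 5 both say at least, and a child who reaches 300 mg also satisfies the hypothesis. This stands. A reader might infer that the child in the example must end as a non-success, but the text does not say so. What remains is that meeting the floor does not guarantee success. The dose-scale powers in step 4 are likewise powers at the minimum effect.

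*The paired t-test may be a between-arm test.* With blocks of 2 by age and sex, and the terms cases and controls in section 5, the pairs could be matched treated and control children. The reading is possible but weak: the recruitment part of section 4 stratifies by sex only, and the later paired test in section 5 is against baseline. Even if accepted, a paired t-test does not suit a three-category outcome. The blocks do raise a question that Fisher's test leaves open, namely whether the stratification or pairing enters the analysis.

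*Power may be ample.* The milk study reports that "our preliminary results reveal an almost 80% success rate". Carried over to egg as an assumption, 80% gives 94% or more for control rates up to 20%. If the 68% resolution by age 16 in section 3.ii is spread evenly from birth (also an assumption), 1 − 0.32^(1/16) = 6.9% a year; against a 7% control rate, power is 99.7% for a treated rate of 80% and 90% for 60%. A 50-percentage-point reading gives 79% to 88% for control rates of 5% to 40%, though it conflicts with the 40-to-60 mg example. All this stands against any claim of low power. It does not supply the missing basis, because section 5 uses none of these figures.

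**Conclusion.** The mismatch is established by the text: the power basis and the primary variable are different quantities, and no suitable between-arm test is named for the primary variable. The stated 80% is neither confirmed nor refuted.

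Two stronger readings are not supported. A reader might conclude that the trial is underpowered; that depends on 300 mg success rates the plan does not state, and across the assumed rates in the table power runs from 5% to above 99%. A reader might also conclude from reference 75 that the 50% has no basis at all; the title shows only that the citation does not fit, and it may be a slip.

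Whether controls are assessed for 300 mg at 1 year is a separate point. The visible text describes no such challenge for them, but the study schema is not shown. It should be confirmed, and nothing here depends on it.

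**What to change.** 1. Reconcile the hypothesis and superiority statement in section 3.ii, the primary variable in section 4 and the sample-size sentence in section 5, so that one outcome is primary. The choice is the sponsor's.
2. If the section 4 variable stands, replace the paired t-test for the primary outcome with a between-arm test of 300 mg success at 1 year, for example Fisher's exact test, and say whether the stratification or pairing is used in the analysis. Keep the paired and two-sample t-tests for the laboratory and skin-test measures. If tolerated dose is made primary, name a between-arm test, state its scale, SD and source, and restate the power.
3. If the section 4 variable stands with Fisher's test, replace the power sentence with: *17 per arm give about 80% power (Fisher's exact test, two-sided 5%) for total desensitization of 37% vs 0%, 50% vs 5%, 59% vs 10% or 71% vs 20%; all rates are assumptions.*
4. Correct or remove reference 75 at this point.

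Cost: wording only, with no added patients. The downside is that the restated power openly depends on assumed rates and is below 80% under some of them (63% for 50% vs 10%, 32% for 50% vs 20%). The plan should also say how children without a 1-year result are counted. Counting them as non-successes keeps 17 per arm but lowers both rates and the power: if one in six were missing (assumed), 60% vs 10% becomes 60 × 5/6 = 50% vs 10 × 5/6 = 8.3%, and power falls from 83% to about 69%.

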The rising incidence of food allergies is occurring more rapidly than changes to the genome sequence would allow ⁽⁵⁵⁾ and epigenetic regulation (heritable changes in gene expression that occur in the absence of alterations in DNA sequences) may in part mediate the complex gene-by-environment interactions that can lead to asthma. ⁽⁵⁶⁾ Experimental studies provide substantial in vitro data indicating that DNA methylation of genes critical to T-helper cell differentiation may induce polarization toward or away from an allergic phenotype. Methylation of DNA and resulting changes in chromatin structure have been shown to initiate the process by which the Th cells lose their plasticity and differentiate productively toward the Th1 versus the proallergic Th2 pattern

of cytokine gene expression.⁽⁵⁷⁻⁵⁹⁾ So far no studies have explored the role of DNA methylation in short term processes such as desensitization for food allergens.

3.vii. Gaps in role of allergen specific salivary IgA.

We hypothesize that development of an enhanced antigen specific mucosal IgA response is associated with reduced responses to oral antigen challenge in food allergy in children. Antigens delivered to the gastrointestinal mucosa are subject to a variety of barriers before they come into contact with effector cells such as mast cells, loaded with antigen specific IgE, that may trigger an adverse allergic reaction. Since the majority of allergic effector cells within the intestinal tract are below the epithelial barrier, and IgA is in much higher concentration than IgE, we may enhance blockade against allergic reactions in previously sensitized individuals through increases in mucosal IgA, and especially through an increased IgA:IgE ratio. While this has been examined experimentally in mice, the relationship between mucosal IgA and desensitization in the clinical setting is not defined.

4. Methodological Approach/Study Design

Thirty four boys and girls with between 6 to 18 years of age, diagnosed with egg allergy will be approached by our study group. Participants will be recruited from the allergy clinic at the Montreal Children's Hospital.

Inclusion criteria: Children 6 years and older who satisfy all the following criteria will be included:

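### The 80% power for 17 + 17 is tied to paired t-tests, which do not make the randomised comparison; between arms, 17 per group reach 80% only at a standardised difference of 0.99

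*Combined protocol and SAP*

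**What the plan says.** The sizing paragraph in section 5 (Statistical Considerations) starts from the statement that "previous studies in adults have attributed at least 50% improvement in the ability to tolerate egg", adds alpha 0.05 and power 0.80, and concludes: "a sample of 17 cases and 17 controls will be recruited. Statistical analyses will be performed using paired t-tests". Section 4 gives the same total: "Thirty four boys and girls with between 6 to 18 years of age".

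The design paragraph in section 3.ii describes a 1:1 randomised trial "aiming to demonstrate superiority of the desensitization protocol to an avoidance strategy regarding the tolerated quantity of egg". It explains the 50% by example: "a child that was able to tolerate only 40 mg of merengue will be able to tolerate at least 60 mg".

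The next paragraph of section 5 does name a two-sample t-test against control, but only for sIgE, sIgG, weal size, mast cell, salivary IgA, T cell and DNA methylation measures. Tolerated egg is not in that list. The significance rule is "A P value of <0.05 will be considered significant", with no statement of one- or two-sided testing.

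Under Variables measured in section 4, the primary variable is a three-category desensitization status at 1 year, with only the 300 mg category counted as success.

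**The concern.** A power figure belongs to a particular test of a particular contrast. Here the contrast of interest is between randomised arms, while the only test named for tolerated egg is paired. The ordinary meaning of a paired t-test, and the one section 5 uses when it compares biomarkers with their baseline values, is a within-child comparison. Applied to the treated arm, such a test uses no control data and cannot separate the effect of desensitization from natural resolution, which section 3.ii itself discusses.

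Two misreadings follow. A significant before-after change in treated children could be reported as superiority. A non-significant difference between arms could be taken as evidence against desensitization from a trial believed to have 80% power for that comparison, when the plan does not show that it has.

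**Working it through.** **Inputs from the protocol.** Alpha 0.05, power 0.80, 17 per arm, 34 in total and 1:1 allocation (sections 3.ii, 4 and 5). The effect is a relative rise of at least 50%, such as 40 mg to 60 mg. Not given: the SD of tolerated quantity or of its change, success rates, sidedness, dropout and the formula used.

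**Assumptions.** Two-sided testing. Let d be the mean change in treated children divided by the SD of change. For the between-arm test, take the same SD in both arms and no mean change in controls, so that d is also the standardised difference between arms. No dropout.

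**Can the stated 17 + 17 be reproduced?** Not from the stated inputs alone: a 50% relative improvement fixes d only once an SD is known. If the SD of change equals 50% of baseline, d = 0.5/0.5 = 1.0; if it equals 100% of baseline, d = 0.5/1.0 = 0.5. Several unstated inputs do return the stated numbers:
- two-sample t-test at d = 1.0: 16.7, so 17 per arm (power 80.7%);
- paired t-test at d = 0.5: 33.4, so 34 pairs (power 80.8%), which equals the trial total;
- two success rates 50 points apart: 10% versus 60% with continuity correction gives 17 per arm.

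Since more than one route fits, the match does not identify the one used.

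**Power with 17 per arm (noncentral t).**
- Paired test on 17 children: noncentrality d × √17 = 4.123d, 16 degrees of freedom, critical value 2.120.
- Two-sample test, 17 per arm: noncentrality d × √(17/2) = 2.915d, 32 degrees of freedom, critical value 2.037.

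| d | Paired, 17 pairs: noncentrality, power | Two-sample, 17 per arm: noncentrality, power |
|---|---|---|
| 0.50 | 2.06, 49.1% | 1.46, 29.3% |
| 0.72 | 2.98, 80% | 2.11, 53% |
| 0.99 | 4.09, 97% | 2.89, 80% |
| 1.00 | 4.12, 97.2% | 2.92, 80.7% |

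Rows 0.72 and 0.99 use the unrounded values 0.724 and 0.991 that give exactly 80%. At d = 0.5, 80% power would need 34 pairs, or 64 per arm for the two-sample test (63.8 rounded up).

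**Primary variable.** Success at 300 mg is a different calculation. For an assumed 50-point difference, Fisher's exact test with 17 per arm has 82.7% power at 10% versus 60%, 79.2% at 20% versus 70%, 79.0% at 25% versus 75% and 79.2% at 30% versus 80%. The protocol states none of these rates.

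**The case against.** A reader might go further and infer that 34 was calculated as 34 before-after pairs at d = 0.5 and then wrongly split into two arms, so that 80% power holds for neither test (49% paired, 29% between arms). Those percentages are correct at d = 0.5, but the documents do not support the inference. No section states an effect of 0.5 SD; section 3.ii defines the 50% in milligrams. No section calls 34 a number of pairs. A two-sample t-test at d = 1.0 gives the stated 17 per arm directly, and at that effect both tests have at least 80% power. The split-pairs origin is one possible explanation and no more.

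A second objection is that the pairs may be matched children, since section 3.ii speaks of randomising in groups of 2 by age and sex. A paired test on 17 treated-control pairs would be a between-arm comparison. However, section 5 does not say this, and section 4 describes stratification by sex only. Nor would it supply the missing inputs: 17 pairs still need a mean difference of 0.72 SDs of the within-pair difference. If matching induced no correlation, that equals 0.724 × √2 = 1.02 SDs of the individual changes.

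Third, the primary variable is success at 300 mg, for which power may be good. If success were 80% in treated children (an assumption, taken from the almost 80% reported for the team's milk study) and 10% to 20% in controls (also an assumption), Fisher's exact test with 17 per arm would have 94% to 99% power. This stands. The trial as a whole is therefore not shown to be underpowered; the point is limited to the power statement and to the test of tolerated quantity.

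**Conclusion.** The point holds in a limited form. Without assuming any effect size, section 5 links its 80% to paired t-tests and names no between-arm test for tolerated egg, although section 3.ii sets out a between-arm superiority aim on that quantity. The 80% is unverifiable as written.

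The size of the gap depends on the test: 80% power at a standardised effect of 0.72 for the paired test, but 0.99 for the between-arm test. If the 80% belongs to a paired test in the 17 treated children, the randomised comparison at that same effect has 53% power. These figures rest on two-sided 0.05, equal SDs of change, no mean change in controls and no dropout; the range of 0.5 to 1.0 for d is assumed. It is not shown that power falls below 80%, because at d = 1.0 it does not. The correction is worth making, since it settles which result can support a claim of superiority.

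**What to change.** Keep 17 + 17 and rewrite the sizing paragraph:
- Name a two-sided between-arm comparison as the superiority test for tolerated egg: a two-sample t-test on tolerated quantity or on its change.
- Label the paired t-tests descriptive within-arm analyses.
- Replace the unqualified 80% with: for tolerated quantity, 17 per arm give 80% power for a between-arm standardised difference of 0.99 (53% at 0.72, 29% at 0.5).
- State the SD or success rates assumed and where they come from.
- Give a separate power figure for the primary variable, success at 300 mg. For example, Fisher's exact test with 17 per arm gives about 79% to 83% power for a 50-point difference at assumed control rates of 10% to 30%.

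The cost is one paragraph, with no added patients or procedures. The downside is a less favourable stated detectable effect for tolerated quantity.
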